### 2.1.1 Primary Objective

The primary objective of this study is to determine the diagnostic utility of the BIOMONITOR to detect AF within study subjects who are being evaluated for an ablation. Specifically, the diagnostic sensitivity of the BIOMONITOR will be determined by comparing AF events detected by the BIOMONITOR and 48 hr Holter monitor for each subject. Using the 48 hr Holter monitor as the gold standard, subjects with AF events detected by the BIOMONITOR will be categorized as true positive or false positive.

It is expected that sensitivity will be greater than 90% in detecting AF within study subjects that are being evaluated for ablations.

Diagnostic Sensitivity:

$H_0$ : The Sensitivity (Se) for detecting at least one true positive AF episode per subject will be less than or equal to 90%. ( $Se \leq 90\%$ )

$H_a$ : The Sensitivity for detecting at least one true positive AF episode per subject will be greater than 90% ( $Se > 90\%$ )

A rejection of the null hypothesis would demonstrate that there is evidence that Sensitivity is greater than 90%.

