## 2.4 Sample-Size Analysis

The study is designed to limit the number of subjects involved while still exposing the device to a sufficiently large subject population to evaluate the utility of BIOMONITOR in subjects that are being evaluated for AF ablation. A sample size of 60 subjects with evaluable data sets is required to evaluate the diagnostic sensitivity with the following assumptions:

- Prevalence of AF during Holter test: 50%
- Confidence interval: 95%
- Precision level: 6.35%
- Expected patient-based sensitivity: 97%
- Drop-out rate after 48 hr Holter monitoring is initiated: 8%

To account for expected attrition due to subject withdrawal following consent but prior to completion of the study testing period:

- Up to 100 subjects will be provisionally enrolled
- Assumed 40% drop out rate between consent and the initiation of 48 hr Holter monitoring (e.g. R-wave amplitude <0.25 mV, no AF detection during pre-Holter observation period, withdrawn consent, etc.)
- Sixty subjects will undergo 48 hr Holter monitoring (fully enrolled)

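### The 6.35% precision behind the 60 subjects is a normal-approximation half-width that runs past 100%; with 28 to 30 AF-positive subjects the exact half-width averages about 8 points and the lower arm 13 to 14

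*Protocol*

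**What the plan says.** Protocol section 2.4 (Sample-Size Analysis) lists five planning inputs for the sensitivity objective:

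- "Prevalence of AF during Holter test: 50" percent
- "Confidence interval: 95" percent
- "Precision level: 6.35" percent
- "Expected patient-based sensitivity: 97" percent
- "Drop-out rate after 48 hr Holter monitoring is initiated: 8" percent

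It concludes: "A sample size of 60 subjects with evaluable data sets is required to evaluate the diagnostic sensitivity". Further down, the same section uses 60 for those who start Holter monitoring: "Sixty subjects will undergo 48 hr Holter monitoring (fully enrolled").

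The section names no interval method and gives neither a significance level nor a power. The null hypothesis in section 2.1.1 is: "The Sensitivity (Se) for detecting at least one true positive AF episode per subject will be less than or equal to 90" percent. Section 2.5.1 tests it with a one-tailed binomial test. The precision figure is therefore the only statistical basis the protocol gives for its sample size.

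**The concern.** For a proportion near 97% estimated in a few dozen subjects, a symmetric margin of 6.35 points is suspect on sight, because 97 + 6.35 exceeds 100. That suggests a normal approximation used outside the range where it works.

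The lower side matters most, because the study asks whether sensitivity exceeds 90%. Subtracting 6.35 from 97 gives 90.65%, so section 2.4 can be read as saying that a result on target would leave the lower limit just clear of the benchmark. If the real lower arm is much longer, that reassurance is false. The sponsor and readers would then be planning around a precision that an interval suited to these numbers does not, on average, give.

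**Working it through.** **Inputs** (protocol section 2.4): sensitivity 0.97, precision 0.0635, confidence 95%, prevalence 0.50, drop-out 0.08. Benchmark 0.90 (section 2.1.1). The denominator is the number of Holter AF-positive subjects, as the prevalence input implies.

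**1. Reproducing the 60.** Normal-approximation formula for a half-width d:

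- AF-positive subjects: n = 1.96² × 0.97 × 0.03 / 0.0635² = 27.7
- Evaluable subjects: 27.7 / 0.50 = 55.4
- Subjects starting Holter: 55.4 / 0.92 = 60.3

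This matches the stated 60 (strictly, it rounds up to 61). Using z = 1.645 instead gives about 43, so a two-sided 95% normal-approximation half-width is the reading that fits.

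**2. Whether the approximation is usable.** Expected missed subjects: 28 × 0.03 = 0.84. Implied interval: 97 ± 6.35 = 90.65% to 103.35%. At n = 28 exactly the half-width is 1.96 × √(0.97 × 0.03 / 28) = 6.32 points, and the upper end is still 103.3%.

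**3. Exact (Clopper-Pearson) two-sided 95% intervals at n = 28.** Probabilities are for a true sensitivity of 97%.

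| Detected | Probability | Interval | Lower arm (points) |
|---|---|---|---|
| 28/28 | 0.43 | 87.7% to 100% | 12.3 |
| 27/28 | 0.37 | 81.7% to 99.9% | 14.8 |
| 26/28 | 0.15 | 76.5% to 99.1% | 16.4 |

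**4. Average over all results.** The number detected is taken as Binomial(n, 0.97). Half-width is half the full width; the lower arm is the estimate minus the lower limit.

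| AF-positive | Method | Mean half-width | Mean lower arm |
|---|---|---|---|
| 28 | Clopper-Pearson | 8.4 | 14.1 |
| 28 | Wilson | 7.9 | 13.6 |
| 30 | Clopper-Pearson | 8.0 | 13.4 |
| 30 | Wilson | 7.6 | 12.9 |

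At n = 28 the mean exact lower limit is 97 − 14.1 = 82.9%, against the 90.65% implied by section 2.4.

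The row with 30 applies if 60 is the number of evaluable subjects (60 × 0.50). The row with 28 applies if 60 is the number starting Holter (60 × 0.92 × 0.50 = 27.6). Letting the AF-positive count vary at random gives a mean exact lower arm of 14.5 points with 55 evaluable subjects and 13.6 with 60, so the picture does not change.

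**The case against.** The strongest reply is that 6.35% appears in a list of assumptions and makes no promise about a lower limit, and that precision normally means a half-width. Like for like, the gap is then 8.4 or 7.9 points against 6.35, about 1.2 to 1.3 times. This stands, and it limits the point. Setting the 14-point lower arm against 6.35 as a ratio would compare unlike quantities. The same mismatch affects any estimate of how many more subjects would bring the lower arm down to 6.35.

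Three stronger readings are tempting, and the protocol supports none of them:

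- **That no valid 95% interval could have this precision.** This is false. At 28/28, the most likely single result, the exact half-width is (100 − 87.7) / 2 = 6.2 points, and the Jeffreys interval averages 6.7 points at n = 28.
- **That the study will report intervals with poor coverage.** A symmetric interval would cover a true 97% in only about 57% of studies at n = 28, because it collapses to a single point at 28/28. But the protocol plans no such interval. Section 2.5.1 specifies a binomial test, and the formula in section 2.4 is inferred from its inputs.
- **That the primary test is bound to fail, because 28/28 has a lower limit below 90%.** That limit is two-sided, the test is one-tailed, and the protocol states no level. At an assumed one-sided 5%, the exact lower limit is 89.9% for 28/28 but 90.5% for 30/30. Power is a separate question.

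The choice of interval for reporting can also be left to the statistical analysis plan. What survives is that the one precision figure printed in the protocol, from which the sample size is derived, comes from an approximation that breaks down at this size.

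**Conclusion.** The point holds in a limited form. The 6.35% is a normal-approximation half-width applied where 0.84 missed subjects are expected, and the interval it implies ends above 100%. For 28 to 30 AF-positive subjects and a true sensitivity of 97%, the two-sided 95% half-width averages about 8 points (7.6 to 8.4 across Clopper-Pearson and Wilson), and the lower limit falls on average about 13 to 14 points below the estimate. Section 2.4 implies a lower limit just above 90%; the exact mean at n = 28 is about 83%, and even a perfect 28/28 gives 87.7%.

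This rests on the protocol's own 97%, 50% and 8%, on Holter AF-positive subjects as the denominator, and on the inference that the unnamed method is the symmetric formula, which the reproduced 60 supports. The correction is worth making because the figure is the sole stated ground for the sample size and errs on the side that matters. It is not critical: enrolment, procedures and the primary test are untouched by it.

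**What to change.** Keep the enrolment figures. In section 2.4, delete the 6.35% precision line and replace it with a statement to this effect:

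*With about 28 to 30 AF-positive subjects and an expected sensitivity of 97%, the exact two-sided 95% confidence interval is expected to have a half-width of about 8 points and to reach about 13 to 14 points below the estimate (for example, 27 of 28 detected: 81.7% to 99.9%).*

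Settle in the same edit whether 60 counts evaluable subjects or subjects starting Holter, since that decides between 30 and 28 AF-positive. Any interval reported for sensitivity should be exact or Wilson, not symmetric; this can be specified in the statistical analysis plan.

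The cost is a change of wording and a less favourable stated precision. No extra subjects and no change of procedure are needed.

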## 2.5 Data Analyses

Descriptive statistics will be used to present and summarize the data collected in the clinical study. Frequency distributions and cross tabulations will be presented for discrete variables. Means, standard errors, and ranges will be presented for continuous variables.

### 2.5.1 Objective Analysis

The primary objective analysis will calculate the diagnostic sensitivity of the BIOMONITOR. Diagnostic sensitivity is the ability of the BIOMONITOR to correctly identify subjects who have AF as determined by the Holter monitor.

Specifically, diagnostic sensitivity is determined as:

$$\text{Diagnostic sensitivity} = \frac{\text{Number of TP patients}}{\text{Number of TP} + \text{Number of FP patients}}$$

Where TP is true positive and FP is false positive.

To test the primary hypotheses, sensitivity will be calculated and a one-tailed binomial test will be implemented to determine if there is evidence to support the rejection of the null hypothesis.

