### 2.5.2 Analysis for Data of Interest

Additional data of interest, which includes the characterization of the insertion procedure and device functionality, will be analyzed quantitatively and statistically where appropriate. All available results will be categorized and summarized.

Data from the 48 hr Holter recording will support metrics including sensitivity, specificity, positive predictive value, and negative predictive value. Holter monitoring will be used as the gold standard for AF detection. Sensitivity is defined as the proportion of true positives that are correctly identified as positive. Specificity is defined as the proportion of true negatives that are correctly identified as negative. The positive predictive value is defined as the proportion of positive detected episodes that are true positive. The negative predictive value is defined as the proportion of negative detected episodes that are true negative. Evaluation may be performed on an episode, subject, or duration basis. Additional, non-AF episodes recorded on the BIOMONITOR may be compared to Holter data to confirm the onset of different arrhythmias.

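### The primary endpoint formula, TP/(TP+FP), is positive predictive value, not sensitivity, so missed AF does not enter the primary test as printed

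*Protocol*

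**What the plan says.** Section 2.5.1 of the protocol first defines the primary quantity in words: "Diagnostic sensitivity is the ability of the BIOMONITOR to correctly identify subjects who have AF as determined by the Holter monitor". It then prints a formula with the number of TP patients over the number of TP plus FP patients, and explains the symbols: "Where TP is true positive and FP is false positive". The result goes straight into the only hypothesis test: "sensitivity will be calculated and a one-tailed binomial test will be implemented".

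Section 2.1.1 sets the null at sensitivity of 90% or less and says "A rejection of the null hypothesis would demonstrate that there is evidence that Sensitivity is greater than 90" per cent. The same section, and the Summary in the same words, describe the classification this way: "subjects with AF events detected by the BIOMONITOR will be categorized as true positive or false positive". Neither place mentions false negatives.

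Section 2.5.2, on the additional metrics, gives this definition: "The positive predictive value is defined as the proportion of positive detected episodes that are true positive".

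Section 2.4 states "A sample size of 60 subjects with evaluable data sets is required to evaluate the diagnostic sensitivity". Its assumptions include "Prevalence of AF during Holter test: 50" per cent, expected sensitivity 97%, precision 6.35%, a 95% confidence interval and 8% drop-out after Holter initiation.

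**The concern.** Sensitivity conditions on the reference standard. Its denominator is every subject with AF on Holter, whether or not the device detected it (TP + FN). The printed denominator is every subject with a device detection (TP + FP). That is the ratio section 2.5.2 calls positive predictive value, counted in patients instead of episodes.

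If the formula is followed as printed, the study tests predictive value against 90% and reports it as sensitivity. A device could miss AF patients at no cost to the primary endpoint, and one that found every AF patient could fail because of a few false alarms. The stated question, whether sensitivity exceeds 90%, would not be answered.

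**Working it through.** **1. Which denominator the sample size assumes.** Inputs from 2.4: Se = 0.97, precision d = 0.0635, z = 1.96, Holter AF prevalence 0.50, drop-out 0.08.

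- AF-positive subjects needed: z² × Se × (1 − Se) / d² = 1.96² × 0.97 × 0.03 / 0.0635² = 27.7
- Evaluable subjects: 27.7 / 0.50 = 55.4
- Subjects starting Holter: 55.4 / 0.92 = 60.3, which matches the stated 60.

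Dividing by the prevalence of AF on Holter makes sense only if the denominator is Holter-AF-positive subjects, that is TP + FN. The study was sized for true sensitivity.

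**2. What the two ratios give.** The test is exact binomial, one-sided, with null value 0.90. Section 2.5.1 states no alpha; 0.05 is assumed here.

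| TP | FN | FP | Sensitivity TP/(TP+FN) | p | Printed TP/(TP+FP) | p |
|---|---|---|---|---|---|---|
| 29 | 1 | 0 | 29/30 = 96.7% | 0.184 | 29/29 = 100% | 0.047 |
| 30 | 0 | 1 | 30/30 = 100% | 0.042 | 30/31 = 96.8% | 0.170 |
| 20 | 8 | 0 | 20/28 = 71.4% | 0.999 | 20/20 = 100% | 0.122 |
| 28 | 0 | 5 | 28/28 = 100% | 0.052 | 28/33 = 84.8% | 0.894 |

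The p-values in the first two rows:

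- 29 of 29: 0.9^29 = 0.047
- 29 of 30: 0.9^30 + 30 × 0.1 × 0.9^29 = 0.042 + 0.141 = 0.184 (before rounding the terms)
- 30 of 30: 0.9^30 = 0.042
- 30 of 31: 0.9^31 + 31 × 0.1 × 0.9^30 = 0.038 + 0.131 = 0.170 (before rounding the terms)

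In row 1 the printed formula rejects the null and the correct one does not. In row 2 it is the other way round. In rows 3 and 4 neither version rejects, but the reported estimate is wrong by 29 and 15 percentage points.

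**3. How many misses can be hidden.** With no false positives, the printed formula rejects once there are 29 true positives, whatever the number of false negatives. With 30 AF-positive subjects that hides one miss. If 40 of about 55 evaluable subjects were AF-positive (73%, an assumption above the planned 50%), 29 TP and 11 FN would still give 29/29 and p = 0.047, with true sensitivity 29/40 = 72.5%.

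**4. Whether the two quantities can differ in practice.** Section 1.2.1 reports sensitivity 95.4% and positive predictive value 76.3% for the first-generation device, a gap of 19.1 points with the 90% threshold in between.

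**The case against.** The words in 2.5.1, the hypotheses and the sample size all describe true sensitivity, so the protocol contradicts itself rather than choosing predictive value. This is right, and it supports correcting the formula.

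The sentence sorting device-positive subjects into TP or FP is literally true of any two-by-two table and defines no denominator. The Summary only repeats 2.1.1. This also stands: the sentence is incomplete rather than false. It does mean, however, that no text on the primary endpoint supplies the missing false negatives.

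Sensitivity also appears among the additional metrics in 2.5.2, possibly at subject level, so missed AF is not lost from the study altogether. It is absent from the primary endpoint as printed.

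The effect on the test is limited at planned numbers. With 28 AF-positive subjects even 28/28 gives p = 0.9^28 = 0.052, so neither version can reject at 0.05. With 30, at most one miss is hidden. At a one-sided alpha of 0.025, 36 of 36 would be needed (0.9^35 = 0.02503; 0.9^36 = 0.0225). Hiding many misses needs AF prevalence above 50%. That is possible, because 3.1.4 removes subjects with no AF in the observation period, but it is not the planning assumption.

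The earlier study used an older device and compared episode by episode, with wide spread (± 13.3% and ± 38.7%). Its gap shows that the two measures can differ; it does not forecast this study.

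None of these points makes TP/(TP+FP) a sensitivity.

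**Conclusion.** The formula is wrong as written. It conflicts with the definition directly above it, with the hypotheses in 2.1.1 and with the sample size in 2.4. It is the only formula given for the only primary objective.

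Near the planned number of AF-positive subjects (30, half of 60), a single false negative or a single false positive is enough to change the test result, assuming one-sided alpha 0.05. The estimate can be wrong by far more: with 28 AF-positive subjects, eight misses are reported as 100% instead of 71.4%. These tables are illustrations, not predictions. The finding that the ratio is mislabelled depends on neither alpha nor prevalence.

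The protocol fixes the formula, so a different denominator in the SAP would contradict it, and a choice made after seeing the data would look post hoc.

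**What to change.** - **Section 2.5.1:** replace the formula with TP/(TP+FN). Define TP as a subject with Holter AF and at least one matching BIOMONITOR AF detection, and FN as a subject with Holter AF and no matching detection. State that the binomial denominator is all evaluable Holter-AF-positive subjects.
- **Section 2.1.1 and Summary:** change the last sentence of the objective so that Holter-AF-positive subjects are classed as true positive or false negative.
- **Section 2.5.2:** keep TP/(TP+FP) as positive predictive value among the data of interest.
- **SAP:** make the same correction if it carries the formula.

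The cost is a wording change in three places of the protocol. N = 60 is unaffected, because 2.4 already uses the correct denominator, and the Holter and BIOMONITOR data already planned are sufficient. The correction should be dated before the primary analysis, which 2.5.4 places at the interim look once Holter visits are complete. It does not address the separate limit that about 28 AF-positive subjects leave the exact test unable to reject at 0.05.

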### 2.5.2 Analysis for Data of Interest

Additional data of interest, which includes the characterization of the insertion procedure and device functionality, will be analyzed quantitatively and statistically where appropriate. All available results will be categorized and summarized.

Data from the 48 hr Holter recording will support metrics including sensitivity, specificity, positive predictive value, and negative predictive value. Holter monitoring will be used as the gold standard for AF detection. Sensitivity is defined as the proportion of true positives that are correctly identified as positive. Specificity is defined as the proportion of true negatives that are correctly identified as negative. The positive predictive value is defined as the proportion of positive detected episodes that are true positive. The negative predictive value is defined as the proportion of negative detected episodes that are true negative. Evaluation may be performed on an episode, subject, or duration basis. Additional, non-AF episodes recorded on the BIOMONITOR may be compared to Holter data to confirm the onset of different arrhythmias.

### 2.5.3 Analysis Population

The analysis population for the primary objective includes all subjects that are enrolled in the study and have evaluable 48 hr Holter data and BIOMONITOR data. If an evaluable 48 hr Holter contains segments which are marked as not interpretable by the Holter Core Laboratory, these segments will be excluded from analysis. Subjects may be allowed to repeat 48 hr Holter monitoring if the Holter Core Laboratory determines a significant portion of the recording is uninterpretable.

Evaluable BIOMONITOR data is defined as successful collection of the complete BIOMONITOR data set from the 48 hr Holter period. In the event that some BIOMONITOR detections are not available due to the number of detected events exceeding the device storage capacity, the segments with missing BIOMONITOR information will be excluded from the analysis.

Data of interest elements that require comparison to the 48 hr Holter monitor data will use the same analysis population. Analysis for additional data of interest will be completed with both provisionally enrolled and fully enrolled study populations.

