## 12. APPENDIX A: DEFINITION OF TERMS

**CFR** – Code of Federal Regulations

**Device Damage** – Visible damage to the antenna or device body or mechanical malfunction that leads to the inability of the device to correctly sense the heart signals.

**Device Failure** – Inability of the device to correctly sense the heart signals, not attributable to a mechanical malfunction that remains unresolved despite reprogramming and/or repositioning.

**Device Migration** – Visual, radiographic, electrical or electrocardiographic evidence of device displacement from the original implant site or electrode displacement that adversely affects device performance or subject health.

**Device Protrusion** – Device or antenna perforation through the skin that is not a result of skin erosion.

**Device Rejection Phenomena** – Reaction to device materials; includes local tissue reaction and metal sensitivity.

**Excessive Bleeding** – Bleeding during the insertion procedure that cannot be stopped by applying pressure alone.

**Fluid Accumulation within the Device Pocket** - Fluid swelling within the insertion site that is not related to infection or considered to be a hematoma, which requires surgical intervention to resolve.

**Hematoma** – An accumulation or persistent swelling of blood that requires evacuation, drainage, post-insertion hospitalization, or blood transfusion.

**Holter Monitor** – A battery-operated portable device that measures and records your heart's activity (ECG) continuously for 24 to 48 hours

**Inability to insert BIOMONITOR** – BIOMONITOR insertion was attempted but not successfully placed.

**Long-standing Persistent AF** – Long-standing persistent AF is defined as continuous AF of greater than 12 months' duration.

**Non-healing Pocket Dehiscence** – Separation of wound edges around the insertion site of the device that has not healed; excludes hematoma, seroma, infection, and erosion.

**Paroxysmal AF** – Paroxysmal AF is defined as AF that terminates spontaneously or with intervention within 7 days of onset.

**Permanent AF** – Permanent AF is defined as the presence of AF that is accepted by the patient and physician, and for which no further attempts to restore or maintain sinus rhythm will be undertaken. The term permanent AF represents a therapeutic attitude on the part of the patient and physician rather than an inherent pathophysiological attribute of AF.

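### The primary population requires a completely collected BIOMONITOR data set, so a Holter-AF subject whose device delivers nothing is dropped rather than counted as not detected, which tends to raise sensitivity

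*Protocol*

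**What the plan says.** Section 2.5.3 defines the primary population as "all subjects that are enrolled in the study and have evaluable 48 hr Holter data and BIOMONITOR data". It then adds: "Evaluable BIOMONITOR data is defined as successful collection of the complete BIOMONITOR data set from the 48 hr Holter period". Both conditions apply to the whole subject.

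The section makes one exception on the device side. When detections are lost because device storage was exceeded, "the segments with missing BIOMONITOR information will be excluded from the analysis", and the subject stays in.

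Section 2.5.1 states the target in words: "Diagnostic sensitivity is the ability of the BIOMONITOR to correctly identify subjects who have AF as determined by the Holter monitor". The hypotheses in Section 2.1.1 set this per-subject sensitivity against 90%, and Section 2.5.1 says that "a one-tailed binomial test will be implemented".

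Table 1 in Section 2.2 defines an enrolled subject by, among other things, the start of Holter monitoring. It places every such subject in the analysis population and does not mention evaluable data.

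Nowhere does the protocol count a Holter-AF subject without a complete device data set as not detected. It does not separate loss caused by the device from loss caused by site handling.

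**The concern.** Sensitivity asks what share of reference-positive subjects the index test finds. The reference standard, here the Holter, should therefore decide who is in the denominator. Section 2.5.3 also requires that the device under test delivered a complete record. If the device stops recording or cannot be read out, a subject with AF on the Holter was not identified, yet the subject disappears instead of counting against the device.

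This is a stated rule about who is analysed, not a detail left for a later document. It bears on the primary result because the number of AF-positive subjects is small. With about 30 of them, each subject is worth about 3.3 percentage points, and the exact test against 90% can turn on a single one.

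**Working it through.** **Inputs.** From Section 2.4: 60 subjects, AF prevalence during Holter 50%, expected sensitivity 97%, precision 6.35%, 95% confidence, 8% drop-out after Holter start. From Section 2.1.1: null value 90%. From Section 2.5.1: one-tailed binomial test. The protocol states no alpha; one-sided 0.05 is assumed. It gives no rate of device-caused loss; 0 to 2 AF-positive subjects are assumed. Sensitivity is computed as TP/(TP+FN), following the verbal definition.

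**The plan's own figure.** AF-positive subjects needed: 1.96² x 0.97 x 0.03 / 0.0635² = 27.72. Divided by 0.50 this is 55.45, and divided by 0.92 it is 60.27. The stated 60 reproduces. It corresponds to 60 x 0.50 = 30 AF-positive subjects at Holter start, and 30 x 0.92 = 27.6 after the planned drop-out.

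**Effect of the rule.** Take 30 AF-positive subjects, of whom k have a device-caused non-delivery with no retrieved detection, and all others are detected. Under the plan's rule the result is (30-k)/(30-k), with p = 0.90^(30-k). Counting the failures as not detected gives (30-k)/30, with p = P(X ≥ 30-k) for X ~ Binomial(30, 0.90).

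| k | Excluded (plan) | p | Counted as not detected | p |
|---|---|---|---|---|
| 0 | 30/30 = 100% | 0.042 | 30/30 = 100% | 0.042 |
| 1 | 29/29 = 100% | 0.047 | 29/30 = 96.7% | 0.184 |
| 2 | 28/28 = 100% | 0.052 | 28/30 = 93.3% | 0.411 |

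For k = 1: 0.90^30 + 30 x 0.10 x 0.90^29 = 0.0424 + 0.1413 = 0.184. One subject decides whether the null hypothesis is rejected. For k = 2 neither approach rejects, but the estimates differ by 6.7 points.

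**Where the test can be affected.** At one-sided 0.05 the test needs at least 29 complete AF-positive subjects, all detected (0.90^28 = 0.052 is already too large). With 28 or fewer the rule can inflate the estimate but cannot produce a rejection.

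**Error rate.** Suppose the true detection rate, with failures counted as misses, is exactly 90%, and a share f of the 30 AF-positive subjects have incomplete data with no retrieved detection. Under exclusion, rejection requires k = 0 or 1 and all the rest detected, so P(reject) = 0.90^30 + 30 x f x 0.90^29 = 0.0424 + 1.413f. This is 7.1%, 11.3% and 15.5% for f = 2%, 5% and 8%, against 4.2% when failures count as not detected. The values of f are assumptions.

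**Opposite direction.** The endpoint in Section 2.1.1 needs only one true-positive episode per subject. A device that detected AF and then failed gives an incomplete data set from a subject who is already a true positive, and Section 2.5.3 drops that subject too. If two such subjects are dropped from 29/30 = 96.7%, the result is 27/28 = 96.4%. If they are dropped from 30/30 (p = 0.042), it is 28/28 (p = 0.052).

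**The case against.** A reader might infer that the exclusion can only raise sensitivity. The documents do not support this. As shown above, subjects with a retrieved true-positive detection are dropped as well, and that lowers the estimate or leaves it unchanged and weakens the test. For the same reason, a remedy that counted every incomplete record as not detected would be biased downward.

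A reader might also infer that poor sensing takes a subject out. It does not follow. Section 3.2.7 describes collection as interrogating the device and downloading its episodes and episode list. A device that senses badly and logs no AF can still yield a fully collected, empty list; that subject stays in and counts as a miss. The Appendix A entries that refer to "inability of the device to correctly sense the heart signals" are adverse-event definitions that Section 2.5.3 never invokes.

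Three further objections limit the size:

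- The 8% in Section 2.4 is general drop-out and is not attributed to the device. Subjects have also just passed a 12 to 16 day check of AF episodes and R-wave sensing (Section 3.1.4), so failure in the next few days is plausibly uncommon.
- At the plan's own expected yield of 27.6 AF-positive subjects after drop-out, the test cannot reject at the assumed alpha. Only the estimate is then exposed.
- The formula printed in Section 2.5.1 has FP where FN belongs. Taken literally, an undetected Holter-AF subject never enters it and the exclusion has no effect. That is a separate error; this point rests on the verbal definition and the hypotheses.

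It can also be said that worst-case tables belong in an analysis plan, which is not shown. That is fair for the tables, but the population rule itself is fixed in the protocol.

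What remains is that a Holter-AF subject for whom the device delivered nothing is removed, although the stated question would count that subject as not identified.

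**Conclusion.** The point holds as a tendency, not as a one-way bias. Section 2.5.3 makes membership of the primary population depend on the index test having delivered a complete data set, which does not match the target in Section 2.5.1. For subjects with no retrieved detection the effect is upward: with 30 AF-positive subjects and all others detected, 3.3 points for one such subject and 6.7 points for two. One can be enough to move the test from p = 0.184 to p = 0.047.

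This rests on assumed figures: 0 to 2 device-caused losses, one-sided 0.05, and TP/(TP+FN). With 28 or fewer complete AF-positive subjects, only the estimate is inflated. The rule should be changed before the primary analysis; it does not invalidate the design.

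**What to change.** In Section 2.5.3, define the primary denominator by the reference standard: every fully enrolled subject with an evaluable Holter that shows AF. Reconcile this with the enrolled-subject entry in Table 1. Then classify each such subject as follows:

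- **Detected**, if any retrieved BIOMONITOR detection matches Holter AF, even when the data set is incomplete.
- **Not detected**, if the data set is complete without a matching detection, or if the device caused the non-delivery and no matching detection was retrieved.
- **Excluded**, only for a documented handling error, such as a lost file or a download not done.

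Record the cause of absent or incomplete device data on the Holter Completion eCRF. Report two further results beside the primary one: the current complete-case figure, and a worst case in which all missing device data count as not detected.

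The cost is one paragraph, one reason field and one extra table. The downside is that the reported sensitivity may come out slightly lower.
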